8.1.3 Agent Ordering and Agent Accountability

NCI-supplied agents may be requested by eligible participating Investigators (or their authorized designee) at each participating institution. The CTEP-assigned protocol number must be used for ordering all CTEP-supplied investigational agents. The eligible participating investigators at each participating institution must be registered with CTEP, DCTD through an annual submission of FDA Form 1572 (Statement of Investigator), NCI Biosketch, Agent Shipment Form, and Financial Disclosure Form (FDF). If there are several participating investigators at one institution, CTEP-supplied investigational agents for the study should be ordered under the name of one lead participating investigator at that institution.

Sites can request a 5-vial starter supply of nivolumab. Ipilimumab should not be requested until there is an active patient at the site.

Submit agent requests through the PMB Online Agent Order Processing (OAOP) application. Access to OAOP requires the establishment of a CTEP Identity and Access Management (IAM) account and the maintenance of an “active” account status, a “current” password, and active person registration status. For questions about drug orders, transfers, returns, or accountability,

call or email PMB any time. Refer to the PMB's website for specific policies and guidelines related to agent management.

8.1.3.1 Agent Inventory Records

The investigator, or a responsible party designated by the investigator, must maintain a careful record of the receipt, dispensing and final disposition of all agents received from the PMB using the appropriate NCI Investigational Agent (Drug) Accountability Record (DARF) available on the CTEP forms page. Store and maintain separate NCI Investigational Agent Accountability Records for each agent, strength, formulation and ordering investigator on this protocol.

8.1.3.2 Investigator Brochure Availability

The current versions of the IBs for the agents will be accessible to site investigators and research staff through the PMB OAOP application. Access to OAOP requires the establishment of a CTEP IAM account and the maintenance of an “active” account status, a “current” password and active person registration status. Questions about IB access may be directed to the PMB IB Coordinator via email.

8.2 Commercial Agent(s)

8.2.1 Prednisone

Product description: Prednisone, a synthetic glucocorticoid, is a white crystalline powder. It is available as 1 mg, 2.5 mg, 5 mg, 20 mg, and 50 mg tablets, and as an oral solution. Tablets are available in immediate and delayed release formulations..

Route of administration: Prednisone is administered orally once each day. Delayed release tablet formulations should not be crushed or chewed. Prednisone may be taken with or without food.

Agent Ordering: Oral prednisone will be obtained from commercial sources.

See prednisone package inserts for more information.

8.2.2 Tacrolimus

Product Description: Tacrolimus, (FK506) is a macrolide immunosuppressant produced by *Streptomyces tsukubaensis*. Tacrolimus appears as white crystals or crystalline powder. It is practically insoluble in water, freely soluble in ethanol, and very soluble in methanol and chloroform. Tacrolimus inhibits T lymphocyte activation, although the exact mechanism of action is not known. Tacrolimus binds to FKBP-12, an intracellular protein. A complex of tacrolimus-FKBP-12, calcium, calmodulin, and calcineurin is then formed and the phosphatase activity of calcineurin is inhibited. This effect may prevent the generation of nuclear factor of activated T-cells (NF-AT), a nuclear component thought to initiate gene transcription for the formation of lymphokines (interleukin-2, gamma interferon). The net result is the inhibition of T lymphocyte activation (*i.e.*, immunosuppression). Refer to the package insert for more information.

Availability: Tacrolimus is available for oral administration as capsules containing the equivalent of 0.5 mg, 1 mg, or 5 mg of anhydrous tacrolimus. Inactive ingredients include lactose, hydroxypropyl methylcellulose, croscarmellose sodium, and magnesium stearate.

Storage and Handling: Tacrolimus capsules should be stored at room temperature (15-30 °C, 59-86 °F). Tacrolimus for injection should be stored at 5-25 °C (41-77 °F).

Administration: Capsules should be taken by mouth every 12 hours without food. Immediate-release and extended-release oral formulations are not interchangeable. If a patient cannot take oral capsules, please use sublingual tacrolimus.

Potential drug interactions: Tacrolimus is extensively metabolized by the cytochrome P450 (CYP) system, primarily CYP3A4. Drugs that may increase tacrolimus blood concentrations include: calcium channel blockers (*e.g.*, diltiazem, nicardipine, nifedipine, verapamil), antifungal agents (*e.g.*, ketoconazole, clotrimazole, fluconazole, itraconazole), macrolide antibiotics (*e.g.*, clarithromycin, erythromycin, troleandomycin), gastrointestinal prokinetic agents (*e.g.*, cisapride, metoclopramide), and/or other drugs (*e.g.*, bromocriptine, cimetidine, cyclosporine, danazol, ethinyl estradiol, omeprazole, nefazodone, HIV-protease inhibitors). Drugs that may decrease tacrolimus concentrations include: anticonvulsants (*e.g.*, carbamazepine, phenobarbital, phenytoin), antibiotics (*e.g.*, rifabutin, rifapentine), and/or herbal preparations (*e.g.*, St. John's Wort [*hypericum perforatum*]). Grapefruit and grapefruit juice should be avoided. Refer to an updated reference for current information about drug-drug interactions with calcineurin inhibitors.

Agent Ordering: Tacrolimus will be obtained from commercial sources.

9. STATISTICAL CONSIDERATIONS

9.1 Study Design/Endpoints

9.1.1 Overview

A “success” rate (CR/PR/SD without allograft loss at 16 weeks) of 15% or lower (null hypothesis) would be considered insufficient for further study in this population, while a “success” rate of 40% or higher (alternative hypothesis) would be considered worthy of further investigation. This trial will be performed using a modified Simon’s two-stage minimax design (Simon, 1989). In the first stage, nine patients will be enrolled. To minimize risk to patients, accrual will be paused after the ninth patient is enrolled until a decision is made to continue the trial. If one or no patients experience CR/PR/SD without allograft loss at 16 weeks, the study will be temporarily closed to accrual for futility. Otherwise, 7 additional patients will be enrolled for a total of 16. The null hypothesis will be rejected if 5 or more patients experience CR/PR/SD without allograft loss. This design yields a type 1 error rate of 0.074 and power of 0.8 to distinguish between the null hypothesis and the alternative hypothesis.

9.1.2 Primary Endpoint

The percentage of kidney transplant recipients with selected advanced cancers for whom standard medical, surgical or radiation therapy would be insufficient who experience CR/PR/SD without allograft loss at 16 weeks after administration of nivolumab, tacrolimus, and prednisone.

9.1.3 Secondary Endpoints

- Objective response (CR or PR) rate (ORR) based on RECIST 1.1 criteria, and immune-related objective response rate (irORR) using immune-related response criteria (iRECIST);
- Allograft rejection rate;
- Duration of response among patients who experience CR or PR;
- Progression-free survival;
- Overall survival;

9.2 Sample Size/Accrual Rate

A minimum of 9, and up to 16, patients will be recruited for this study. Estimated accrual is approximately one patient every eight weeks.

The study population is expected to comprise 50% men and 50% women, but because this protocol involves a small number of patients recruited across multiple institutions with geographically, racially, and culturally diverse populations, we cannot estimate the racial composition of the cohort.

PLANNED ENROLLMENT REPORT

Racial Categories	Ethnic Categories				Total
	Not Hispanic or Latino		Hispanic or Latino		
	Female	Male	Female	Male	
American Indian/ Alaska Native					
Asian	1	1			2
Native Hawaiian or Other Pacific Islander					
Black or African American	2	2			4
White	4	4	1	1	10
More Than One Race					
Total	7	7	1	1	16

PHS 398 / PHS 2590 (Rev. 08/12 Approved Through 8/31/2015)

OMB No. 0925-0001/0002

9.3 Stratification Factors

N/A

9.4 Analysis of Primary Endpoints

The percent of kidney transplant recipients who experience CR/PR/SD at 16 weeks and do not experience allograft loss after administration of nivolumab, tacrolimus, and prednisone will be calculated, along with the corresponding exact 95% CI. A minority of subjects treated with immunotherapy may derive clinical benefit and experience a delayed response, stable disease, or increased OS despite initial evidence of PD with nivolumab or combination treatment. Subjects who continue treatment beyond initial investigator-assessed, RECIST 1.1-defined progression will be considered to have investigator-assessed PD at the time of the initial progression event but may be later designated as delayed responses for purposes of determining CR/PR/SD and counted as responses for this study.

The evaluable population for the primary endpoint is all subjects who receive at least one dose of nivolumab and undergo tumor response assessments and graft assessments at ~8 and ~16 weeks. Patients who experience allograft loss within 16 weeks of receiving nivolumab will be evaluable for the primary endpoint even if tumor response assessments cannot be performed. Patients who, in the opinion of the investigator, experience PD (with or without allograft failure) prior to 16 weeks will also be evaluable.

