6.2 Week 16 Assessment

At 16 weeks, patients will be assessed for tumor response to therapy. Patients who experience SD, PR, or CR will be allowed to continue study therapy per Section 6.1 (nivolumab 480 mg IV every 4 weeks for up to 24 doses total). Patients whose disease demonstrates progression will be given 3 options:

1. Reduce or discontinue immunosuppression and continue nivolumab therapy (480 mg IV every 4 weeks for up to 24 total doses) per section 6.1. Dose reductions of immunosuppression will be performed on a case-by-case basis. This option likely increases the risk of allograft loss.
2. Transition to treatment with nivolumab 3 mg/kg IV every 3 weeks for 4 doses + ipilimumab 1 mg/kg IV every 3 weeks for 4 doses, followed by 480 mg nivolumab every 4 weeks for 21 doses per Section 6.3. This option likely carries a higher risk of immune-mediated toxicity compared to nivolumab monotherapy.
3. Discontinue study treatment.

If a patient chooses either option 1 or 2 above, the other option may be used later (*i.e.*, if immunosuppression is decreased and the patient again experiences PD, ipilimumab could be added to therapy or if ipilimumab is added and the patient again experiences PD, immunosuppression could be decreased).

Ideally, patients should be assessed 16 weeks after initiation of nivolumab (regardless of the number of doses received) and complete at least 2 on-treatment scans with the second scan being completed at least 4 weeks after the first scan, before being declared to have PD to allow for the possibility of an immune-related tumor response. However, if, in the opinion of the investigator, a patient demonstrates unequivocal evidence of PD after, for example, 8 weeks of nivolumab therapy, the patient may transition at that time. Additionally, patients who experience delayed disease progression (*e.g.*, an initial objective response followed by PD) may transition at that time.

Patients should transition from nivolumab monotherapy to one of the above 2 options within ~28 days of determination of PD. Patients do not need to be re-screened.

Patients who have experienced allograft loss should discontinue tacrolimus regardless of treatment option chosen. Prednisone may be prescribed as needed.

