11. STUDY CALENDARS

11.1 Nivolumab Monotherapy

Nivolumab monotherapy	Screening	Immuno-suppression adjustment ^A	Treatment (cycle length = 28 days ^B)												Follow-up	Immune-mediated Adverse Reaction ^C	Disease Progression
			Cycle 1		Cycle 2		Cycle 3		Cycle 4		Cycle 5		Cycles 6+				
	Within 28 days of registration	Day -28 to Day 0	Day 1	Day 15	Day 1	Day 15	Day 1	Day 15	Day 1	Day 15	Day 1	Day 15	Day 1	Day 15	See Section 6.8		See Section 6.2
Medication administration																	
Nivolumab (480 mg IV)			X		X		X		X		X		X				
Tacrolimus		X														X	X
Prednisone		X														X	X
Patient medication diary review (Appendix C)		X	X		X		X		X		X		X				
Administrative Assessments																	
Informed consent / HIPAA ^D	X																
Pathology review	X																
Inclusion / Exclusion	X																
Medical History	X																
Record concomitant medications	X		X	X	X	X	X	X	X	X	X	X	X	X	X		
Clinical Assessments																	
Physical examination ^E	X		X	X	X	X	X	X	X	X	X	X	X	X	X	X	
ECOG performance status	X		X		X		X		X		X		X		X	X	
Review of adverse events			X	X	X	X	X	X	X	X	X	X	X	X	X	X	
12-lead EKG and echocardiogram ^F	X ^F																
Efficacy Assessments																	
CT scans: chest / abdomen / pelvis plus additional areas as appropriate	X						X								Day 1 every other cycle (Cycles 5, 7, 9, etc.)	X	
Clinical color photographs with scale ruler of tumors, as appropriate ^G	X		X	X	X	X	X	X	X	X	X	X	X	X			
Brain imaging ^H	X																
Standard-of-care Laboratory Assessments (Note: Day 1 assessments for each cycle may be ± 3 days from scheduled timepoint)																	
CBC w/ differential	X		X	X	X	X	X	X	X	X	X	X	X	X	X		
CMP ^I	X		X	X	X	X	X	X	X	X	X	X	X	X	X		
Dipstick urinalysis ^J	X	X ^K	X	X	X	X	X	X	X		X		X			X	
Pregnancy test ^L	X																
PT/PTT	X																

Nivolumab monotherapy	Screening	Immuno-suppression adjustment ^A	Treatment (cycle length = 28 days ^B)										Follow-up	Immune-mediated Adverse Reaction ^C	Disease Progression
			Cycle 1		Cycle 2		Cycle 3		Cycle 4		Cycle 5		Cycles 6+		
	Within 28 days of registration	Day -28 to Day 0	Day 1	Day 15	Day 1	Day 15	Day 1	Day 15	Day 1	Day 15	Day 1	Day 15	See Section 6.8		See Section 6.2
serum TSH, free T4	X		X	X	X		X		X	X	X	X		X	
Troponin and CPK		X ^K	X		X										
dd-cfDNA collection ^O	X		X	X	X	X	X	X		X	X	X		X	X
Tacrolimus trough level ^R			X		X		X		X		X	X			
Correlative studies															
Serum collection ^M			X		X									X	X

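### Section 9.4 lets patients with RECIST 1.1 progression be counted later as primary successes, with no week-16 limit and no regimen limit

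*Combined protocol and SAP*

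**What the plan says.** Section 9.1.2 defines the primary endpoint as the percentage of patients "who experience CR/PR/SD without allograft loss at 16 weeks after administration of nivolumab, tacrolimus, and prednisone". Objective 1.1.1, the success definition and stage-1 rule in 9.1.1, and the first sentence of 9.4 all use the same 16-week time point.

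Section 9.4 continues with a rule for patients treated past progression. They have PD at the initial event, but "may be later designated as delayed responses for purposes of determining CR/PR/SD and counted as responses for this study". The sentence before it refers to progression on nivolumab or on the combination. Section 9.5 has a nearly identical rule for ORR, which is a best-response endpoint with no fixed time point.

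The final decision rule in 9.1.1 reads: "The null hypothesis will be rejected if 5 or more patients experience CR/PR/SD without allograft loss". Unlike the stage-1 sentence, it does not repeat the 16-week time point.

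Other places bear on the meaning:

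- Section 9.4 makes patients evaluable if they "undergo tumor response assessments and graft assessments at ~8 and ~16 weeks", with exceptions for early graft loss or PD.
- Section 6.2 would ideally have two on-treatment scans "before being declared to have PD to allow for the possibility of an immune-related tumor response". It also says that if "a patient demonstrates unequivocal evidence of PD after, for example, 8 weeks of nivolumab therapy, the patient may transition at that time". One option after PD is "Reduce or discontinue immunosuppression and continue nivolumab therapy"; another is to add ipilimumab.
- The last paragraph of 9.5 treats data from both groups as investigative.
- Sections 9.6.2 and 12.1 apply RECIST 1.1 together with an immune-related version. Neither 9.1.2 nor 9.4 says which one decides a reclassification.

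**The concern.** A landmark endpoint needs a date after which a patient's status cannot change. Section 9.4 fixes that date and then adds a sentence suited to an open-ended best-response endpoint. Taken literally, two kinds of response can enter the primary count although they do not meet 9.1.2: those first seen after week 16, and those seen after the three-drug regimen was changed because of progression.

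The opportunity is real. At one patient every eight weeks (9.2), enrolling the last seven and following them for 16 weeks takes about 64 to 72 weeks (6 × 8 + 16 to 7 × 8 + 16). Stage-1 patients therefore have more than a year in which a PD could be reclassified before the final count. A patient who reduces immunosuppression at about week 8 and stays on nivolumab is, in plain terms, continuing treatment beyond progression.

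The trial is single-arm with investigator-assessed progression, and the conclusion turns on 5 of 16. One patient can decide it.

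**Working it through.** **Inputs.** From 9.1.1: null rate 0.15, alternative 0.40, stage 1 of 9 patients (stop at 1 or fewer successes), total 16, reject at 5 or more, stated type I error 0.074 and power 0.8. Assumed, because the documents give no figure: 40-60% of patients have PD without graft loss, and 5-10% of those are reclassified. As a share q of all patients, that is 0.40 × 0.05 = 0.02 to 0.60 × 0.10 = 0.06, or 16 × 0.02 = 0.32 to 16 × 0.06 = 0.96 patients expected among 16.

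**1. The plan's own figure.** P(reject) = Σ over x = 2..9 of Bin(x; 9, p) × P[Bin(7, p) ≥ max(0, 5 − x)].

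- At p = 0.15 the terms for x = 2, 3, 4 and 5 or more are 0.0192 + 0.0303 + 0.0192 + 0.0056 = 0.0743.
- At p = 0.40 the sum is 0.8149.

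Both agree with the plan.

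**2. How often one patient decides.** P(stage 1 ≥ 2 and total = 4) at p = 0.15 is Σ over x = 2..4 of Bin(x; 9, 0.15) × Bin(4 − x; 7, 0.15) = 0.0544 + 0.0423 + 0.0091 = 0.106.

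**3. Reclassification at the final count only.** Stage 1 is judged on week-16 status. Each week-16 failure is then reclassified with probability q/0.85, which is 0.0235 or 0.0706. To the 0.0743 are added trials that passed stage 1 with a week-16 total of 2, 3 or 4 and gain enough to reach 5:

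| Week-16 total | P(total, passed stage 1) | Added, q = 0.02 | Added, q = 0.06 |
|---|---|---|---|
| 2 | 0.083 | 0.0003 | 0.0059 |
| 3 | 0.137 | 0.0050 | 0.0319 |
| 4 | 0.106 | 0.0263 | 0.0619 |
| P(declare success) | | **0.106** | **0.174** |

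The 0.106 here and the 0.106 in step 2 are separate results that happen to agree.

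**4. Reclassification at both looks.** The counted rate becomes 0.15 + q, so the formula in step 1 applies at p = 0.17 and p = 0.21. It gives **0.114** and **0.221**.

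**5. What the calendar implies.** With 28-day cycles, CT on Day 1 of Cycle 3 falls at (3 − 1) × 4 = 8 weeks. The later entry "Day 1 every other cycle (Cycles 5, 7, 9, etc" starts at (5 − 1) × 4 = 16 weeks. These match the two assessments named in 9.4 and leave room for one reversal, from week 8 to week 16, inside the stated endpoint.

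**The case against.** The strongest answer is that the narrow reading is the natural one. Week 16 is stated in 1.1.1, 9.1.1, 9.1.2 and the opening of 9.4; evaluability in 9.4 is tied to weeks 8 and 16; and the two-scan language of 6.2 explains why a delayed response would be allowed at all. The missing time point in the final rejection sentence is probably shorthand. This stands as evidence of intent. It does not supply the limit, because the sentence in 9.4 permits later designation without one.

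On regimen, the last paragraph of 9.5 names both switching groups, and objective 1.2.2 gives them their own estimates. This also largely stands. But that paragraph sits under secondary endpoints and does not say that these patients stay failures in the primary count, while the lead-in in 9.4 mentions combination treatment, which under 6.3 follows only PD or graft loss.

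On size, the figures in steps 3 and 4 take week-16 status as the quantity being tested. If the inclusive definition were the endpoint and its rate were 15%, a strict stage 1 followed by an inclusive final count would give 0.068 (q = 0.02) down to 0.047 (q = 0.06), below 0.074. A reader might infer that the harm comes from counting differently at the two looks. The figures do not support that: counting reclassified patients at both looks gives the larger values. The harm is departure from the endpoint that 9.1.2 states.

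A reader might also infer that RECIST 1.1 as printed cannot turn PD into SD. It can. Target sums of 100, 125 and 110 mm at baseline, week 8 and week 16 meet PD at week 8 and the SD definition of 12.1.4.1 at week 16. The limit to the period before progression in 12.1.4.3 governs best overall response, not status at week 16. What is missing is only the choice between the two criteria sets.

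**Conclusion.** The point holds and should be fixed. Section 9.4 states a rule that, followed literally, lets responses after week 16 or after a change of regimen for PD count towards the decision at 5 of 16, contrary to the endpoint in 9.1.2.

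It would be wrong to conclude that the stated type I error is in error: 0.074 is correct for the week-16 endpoint, and under the narrow reading applied at both counts it stands. The size is a sensitivity, not a known inflation. At a true week-16 rate of 15%, there is a 0.106 chance of finishing where a single reclassification reverses the conclusion. With an assumed 2-6% of patients reclassified, the chance of declaring success is 0.106-0.174 (final count only) or 0.114-0.221 (both looks), against 0.074. The documents give no rate; 9.4 speaks of a minority who benefit, and 9.5 expects few switchers.

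**What to change.** These changes affect analysis classification only; who may continue, switch or stop is untouched.

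1. In 9.4, state that PD may be reclassified for the primary endpoint, at both the stage-1 and the final count, only on an assessment up to and including the week-16 visit, with a stated window. Name which of the two criteria sets already in use, RECIST 1.1 or iRECIST, decides it.
2. In 9.1.1, add the 16-week time point to the final rejection sentence.
3. In 9.4, cross-refer to the last paragraph of 9.5, so that responses after a post-PD switch to ipilimumab or reduction of immunosuppression are reported under objective 1.2.2 and not in the primary count. The documents favour this choice, through the regimen named in 9.1.2, but do not compel it; if the sponsor prefers another, it should be written down.
4. Report other responses that appear after week 16 under ORR and in the iRECIST summary.

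The cost is two or three sentences, one added phrase and one cross-reference. The downside is that a few genuine late responders move from the primary count to a secondary table.

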1. OBJECTIVES

1.1 Primary Objective

1.1.1 To estimate the percent of kidney transplant recipients with selected advanced cancers for whom standard therapies would be insufficient who, 16 weeks after administration of prednisone, tacrolimus, and nivolumab, experience complete response (CR), partial response (PR), or stable disease (SD) without allograft loss.

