Overall survival (OS) is the time from the first dose of nivolumab to the date of death from any cause. A subject who has not died will be censored at last known date alive. Progression-free survival (PFS) is defined as the time from the first dose of nivolumab to the date of the first documented tumor progression or death due to any cause, whichever occurs first. Subjects who did not progress or die will be censored on the date of their last evaluable tumor assessment. Kaplan-Meier curves will be used to summarize OS and PFS. OS and PFS analyses will be performed for all patients who receive at least one dose of nivolumab.

Because the number of patients who change over to nivolumab + ipilimumab or continue nivolumab with reduction in their immunosuppressive regimen after disease progression on nivolumab monotherapy will be small and unpredictable, data from these patients will be considered investigative and potentially hypothesis-generating.

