9.6.2 Evaluation of Tumor Response

All patients enrolled in the study will be assessed for response to treatment. Tumor responses will be assessed according to RECIST and iRECIST criteria.

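### Section 9.4 drops from the primary denominator treated patients who die by week 16 without progression or graft loss, so any such death raises the reported success percent

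*Combined protocol and SAP*

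**What the plan says.** The primary objective (1.1) begins "To estimate the percent of kidney transplant recipients with selected advanced cancers", and 9.1.2 defines the endpoint as the percentage "who experience CR/PR/SD without allograft loss at 16 weeks after administration of nivolumab, tacrolimus, and prednisone". Neither mentions week 8.

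Section 9.4 reports the percent with an exact 95% confidence interval in a restricted set: "all subjects who receive at least one dose of nivolumab and undergo tumor response assessments and graft assessments at ~8 and ~16 weeks". Two groups are then restored:

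- "Patients who experience allograft loss within 16 weeks of receiving nivolumab will be evaluable for the primary endpoint", even where tumour assessment is impossible.
- "Patients who, in the opinion of the investigator, experience PD (with or without allograft failure) prior to 16 weeks will also be evaluable".

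The section also says that patients treated past initial progression "may be later designated as delayed responses for purposes of determining CR/PR/SD and counted as responses for this study".

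The time-to-event endpoints in 9.5 use a wider set: "OS and PFS analyses will be performed for all patients who receive at least one dose of nivolumab". There, death from any cause is a PFS event. Section 9.6.2 states: "All patients enrolled in the study will be assessed for response to treatment". It gives no denominator and no rule for a patient who is not assessed.

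**The concern.** Section 9.4 names two kinds of failure that stay in the analysis, but not death. A treated patient who dies by week 16 of toxicity or infection, with the graft working and no progression recorded, meets neither exception and has no week-16 assessment. No other section scores or restores that patient for the primary endpoint. Such deaths are foreseeable on the plan's own account: the cardiac guidance in 7.1 says that myocarditis has caused deaths, and the nivolumab risk list in 10.1.1 warns of possibly fatal immune-mediated events.

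Because the primary objective is to estimate this percent, the denominator is part of the primary result. Removing a certain non-success makes the regimen look better than it was among those treated.

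Two related gaps have the same source. There is no rule for a treated patient with unknown week-16 status. And a patient who meets the endpoint at week 16 but missed the week-8 assessment is excluded on the literal wording.

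**Working it through.** **Inputs.** From 9.1.1: null rate 0.15, alternative 0.40, 9 patients in stage 1 (stop at 1 or fewer successes), 16 in total, reject at 5 or more, stated type 1 error 0.074 and power 0.8. From 9.4: percent with exact 95% interval. Assumed: the numbers of successes and of excluded patients, since the documents give no rate for either excluded group.

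**Step 1: the plan's own figures.** P(reject) = sum over x = 2 to 9 of Bin(x; 9, p) × P(Bin(7, p) ≥ 5 − x). At p = 0.15 this gives 0.0743, and at p = 0.40 it gives 0.815. Both agree with 9.1.1.

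**Step 2: who is in the 9.4 set.**

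| Treated patient | In the set? | Week-16 status |
|---|---|---|
| Assessed at both visits | Yes | As observed |
| Graft loss within 16 weeks | Yes | Non-success |
| Progression before week 16 (investigator's opinion) | Yes | Non-success, unless the delayed-response clause later applies |
| Dies by week 16 with neither event | No | Certain non-success |
| No week-16 status, neither event | No | Unknown |
| Assessed at week 16, missed week 8, neither event | No | Known, possibly a success |

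**Step 3: deaths.** With x successes among n treated and k such deaths, the plan reports x/(n − k) instead of x/n. This is larger whenever x ≥ 1 and k ≥ 1. Exact (Clopper-Pearson) 95% intervals for n = 16:

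| Successes | k = 0 | k = 1 | k = 2 |
|---|---|---|---|
| 5 | 31.2% (11.0 to 58.7) | 33.3% (11.8 to 61.6) | 35.7% (12.8 to 64.9) |
| 6 | 37.5% (15.2 to 64.6) | 40.0% (16.3 to 67.7) | 42.9% (17.7 to 71.1) |

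With five successes the shift is 33.3 − 31.2 = 2.1 points for one death and 35.7 − 31.2 = 4.5 for two. The 5/16 interval is 58.7 − 11.0 = 47.7 points wide.

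**Step 4: missing week-16 status.** Take 5 successes among 14 assessed patients and 2 with unknown status. If both were in truth non-successes, the all-treated figure is 5/16 = 31.2% and the reported 35.7% is too high. If both were successes it is 7/16 = 43.8% (19.8 to 70.1) and 35.7% is too low.

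Dropout unrelated to outcome also need not bias upward, because early failures are retained while event-free dropouts leave. Let S be the true rate, d the dropout rate at week 8 and e the share of failures before week 8. The evaluable percent is s/(s + f), with s = S(1 − d) and f = (1 − S)[e + (1 − e)(1 − d)]. For assumed S = 0.40, d = 0.10, e = 0.5: s = 0.36, f = 0.60 × 0.95 = 0.57, and 0.36/0.93 = 0.387. Over d from 5% to 20% and e from 0 to 1, the result runs from 0.400 down to 0.348.

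**Step 5: the week-8 requirement.** If one of 5 week-16 successes among 16 treated missed week 8, 9.4 reports 4/15 = 26.7% (7.8 to 55.1) instead of 5/16 = 31.2%.

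**Step 6: the decision rule.** Section 9.1.1 counts successes among enrolled patients and names no evaluable set. Dropping a non-success without replacement leaves that count as it was, so the Step 1 values stand. They would move only with replacement. If a fraction m of treated patients were excluded failures and were replaced until 16 were evaluable, the null rate among evaluable patients would be 0.15/(1 − m). For assumed m = 5% this is 0.158 and type 1 error is 0.089; for m = 10% it is 0.167 and 0.107.

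**The case against.** The best defence is that the set is openly pre-specified and keeps both main failure modes. Many deteriorating patients will be called progressive in the investigator's opinion and so stay in. Stopping or interrupting drug does not remove a patient either: 6.2 asks for the week-16 assessment whatever the number of doses, and 6.7 continues tumour assessments through dosing interruptions. Deaths remain visible in OS, PFS and the expedited reports under 10.3.3. All of this stands and narrows the gap, but none of it returns the patient who dies without progression or graft loss to the primary denominator. Section 9.6.2 does not do so either, because it states an intention to assess and not how to score the unassessed.

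Two stronger readings are tempting. A reader might infer that every exclusion makes the percent too high. The documents do not support that: unknown status has no known direction (Step 4), and the week-8 requirement can push the percent down (Step 5).

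A reader might also infer that the go/no-go decision or its error rates are compromised. That is not supported either. The rule in 9.1.1 is a count among enrolled patients, and no section provides for replacing treated patients who are not evaluable. The replacement figures in Step 6 show only why the silence should be filled.

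**Conclusion.** As written, the 9.4 rule is wrong for one definable group. A treated patient who dies by week 16 without progression or graft loss is a certain non-success and is removed from the denominator. If any such death occurs and there is at least one success, the percent and both interval limits are too high for the treated population.

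For missing week-16 status the plan lacks a rule, and no direction can be claimed. The week-8 condition is a separate mismatch with the endpoint in 1.1 and 9.1.2.

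The effect is conditional on such patients occurring. It is about 2 points per death and small beside the interval width. The decision rule, type 1 error and power are unchanged provided patients are not replaced. The point merits correction because it touches the primary estimate and needs only wording.

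**What to change.** In 9.4:

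- Use all patients who receive at least one dose of nivolumab as the primary denominator.
- Count death by week 16 as not meeting the endpoint.
- Count absence of week-16 tumour or graft status as not meeting it, labelled as a conservative convention. State the window that qualifies as about 16 weeks: the calendar in 11.1 ties that scan to Cycle 5 Day 1, and cycles can be extended or delayed.
- Do not require the week-8 assessment.
- Keep the present evaluable set as a sensitivity analysis, with the number of treated patients outside it and the reason for each.
- State that treated patients who are not evaluable are not replaced.

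Leave the delayed-response clause as it is. Leave the pause at nine enrolled and the total of 16 in 9.1.1 and 9.2 unchanged, since the pause is an enrolment-based safety measure.

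The cost is wording, with no new assessments. The reported rate may be slightly lower, and withdrawals with unknown outcome are scored against the regimen; the sensitivity analysis shows how much that matters.

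A separate secondary point is that the ORR sets should be reconciled. Section 9.5 needs assessments at both visits (or earlier progression), while 12.1.1.2 needs one cycle and a re-evaluation (or progression within cycle 1).
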